#### **Overview:**

Intervention: Participants in the intervention arm receive -

- Incentives & personal recognitions
- Small Health-promoting Incentive:
  - Choice of a health-promoting tool offered by the caller in the first week of the program. A choice will be provided by the caller between a pedometer and a smart weigh scale of equivalent value. If neither of these options are applicable based on health or other limitations, back-up options will be offered to them (fitness resistant bands or exercise program for upper body fitness). The health-promoting tool will be mailed to participants by approximately the 5th week of the program.
- Personalized recognition of participant by caller ("Personal recognition/Gift"):
  - Callers will select, based on their understanding of the participant, 2 items from a larger pre-selected set of health-related items (related to cooking,

physical activity or sleep), each of equivalent ~\$25.00 value. Callers will select and the program will mail items to the participants between months 1 and 5, to ensure the second item is received within 6 months (Phase 1). Callers will have a deadline to send the first item by the middle of the third month (Month 2.5) and by the middle of the 5th month (Month 4.5)

- Diabetes management information (print) geared to people with low-literacy (Diabetes management materials). This information will be mailed to intervention participants after randomization.
- Communications to support and celebrate the participants learnings:
  - Relationship-building empathetic telephone calls between lay caller and participant. Calls provide an opportunity for participants to discuss whatever they wish to share, and provide support for participants' goals for exercise, nutrition, sleep and medication adherence. In the course of engagement, if the caller feels like the participant can benefit from checking in with their regular clinic provider, they may suggest doing so. In addition, if a participant mentions a social need (such as transportation, food, housing), the caller may suggest some potential social resources for the participant to call. In addition, if the caller feels the participant could benefit from a pre-selected list of YouTube videos, that includes people talking about their life with diabetes, the caller may decide to share it with them. Calls occur 3X a week in first month and 1X a week in subsequent months for 6 months. Participants have agency in informing some aspects of how frequently they're called. After the first week they can adjust calls to a maximum of 5X a week or down to 2X a week (minimum of 2X/week for the first month). After the fourth week all calls shift to weekly. After the 8th week they can adjust calls to 2X every 4 weeks or stay on weekly schedule. Calls average 10 minutes per call or less. The participant may also receive communication via text message about their upcoming phone calls.
  - A letter sent twice in 6 months (Phase 1) to all participants in a callers panel of participants that reflect learnings from participants themselves. No identifiable information will be in these letters.
  - Automated Monthly text messages during months 7-12 (the follow-up phase) with pre-filled customized communications prepared by their caller as simple reminders of tips they discussed during the first 6 months.

**Control:** Participants in the control arm receive –

- Material aspects of elements from the Intervention arm:
- Diabetes management information for people with low literacy (print) at the start of phase 2 (after the 6 month assessment).
- Small health-promoting incentive:

- Choice of a health-promoting tool offered as one of the final questions of the 6 month assessment. A choice will be provided at the end of the 6 month surveys between a pedometer and a smart weigh scale of equivalent value. If neither of these options are applicable based on health or other limitations, back-up options will be offered to them (fitness resistant bands or exercise program for upper body fitness). The tool will be mailed within the 7th month.
- A choice 2 items from the same set of items used for the Intervention arm in Phase 1 related to healthier living, each <\$25/-. This will be offered as one of the final questions of the 6 month assessment. The selected items will be mailed out to the participant in the 8th month and 10th month.
- Participants in the control arm do not receive the communications elements, telephone calls or letters, and otherwise continue with their normal standard of care.
- Participants in the control arm do not receive any text messaging reminders related to the program. To prevent loss to follow-up in the control arm, we will send research study reminder text messages about upcoming measurement appointments.

**Measures:** Primary outcome is Hemoglobin A1C at 6 months (repeated measures at 3 and 6, 9 and 12 months). The measurements will be taken at Lone Star clinic sites, Dell Medical School at The University of Texas at Austin, or other community-based sites, by a member of the research team. Secondary outcomes include Blood pressure through direct measurement and self-reported depression (PHQ-9), anxiety (GAD-7), general mental and physical health (SF-12) and self-reported healthcare utilization and will also be measured at Lone Star clinic sites, Dell Medical School at The University of Texas at Austin, or other community-based sites, by a member of the research team. In addition, process measures include measurements directly from the telephone call system: calls placed/attempted; calls connected (someone spoke); call duration. See below for table of all measures and method of collection.

**Measure Collection:** Biomedical measures will be directly collected in person at their clinic site, Dell Medical School at The University of Texas at Austin, or a community site that is convenient (A1C and Blood pressure). Patient-reported measures will be collected through self-report on a tablet (or paper copy if participant chooses) at the same time biomedical measures are collected. Electronic Health Record measures will be collected via a data agreement with Lone Star Circle of Care (LSCC).

Measure	Freq	ΤοοΙ	
Program Effects			
Hemoglobin A1C	Baseline/3 mths/6 mths/9 mths/12mths	Finger stick on portable device	

Blood Pressure	Baseline/3 mths/6 mths/9 mths/12mths	Automatic blood pressure cuff
Depression	Baseline/3 mths/6 mths/9mths/12 mths	PHQ-9
Anxiety	Baseline/3 mths/6 mths/9 mths/12 mths	GAD-7
General Health	Baseline/3 mths/6 mths/9 mths/12 mths	SF-12
Healthcare Utilization (PCP & BH clinic, Hosp, ED visits)	Baseline/3 mths/6 mths/9 mths/12 mths	Customized (4 new questions added)
Healthcare Utilization (PCP visits, BH visits)	Data pulls for data collected during program	LSCC ElecHealthRecord
Medication Related to DM and HTN	Baseline/3 mths/6 mths/9 mths/12mths	Customized
Medication Adherence Survey	Baseline/3 mths/6 mths/9 mths12 mths	Med Adherence Report Scale (MARS 5)
Diabetes Self-Management	Baseline/3 mths/6 mths/9 mths/12 mths	Perceived Diabetes Self- Management Scale (PDSMS)
Diabetes Self Care	Baseline/3 mths/6 mths/9 mths/12 mths	Summary of Diabetes Self-Care Activities (SDSCA)
Diabetes Self Efficacy	Baseline/3 mths/6 mths/9 mths/12 mths	Stanford Self-Efficacy for Diabetes Scale
Diabetes Distress	Baseline/3 mths/6 mths/9 mths/12 mths	Diabetes Distress Screening Scale
Loneliness	Baseline/3 mths/6 mths/9 mths/12 mths	UCLA 3-item Loneliness Scale
Onset Date of Diabetes	Baseline	Customized
Social Needs Survey	Baseline/6 mths/12 mths	Adapted from PRAPARE
Social Support	Baseline	Lubben Social Network scale
Participant Demographics	Baseline	Customized
Household demographics	Baseline	Customized
Interest in Calling Others	6 mths	Customized
Program Satisfaction	6 mths (intervention arm only)	Customized
Program Improvement	12 mths (intervention arm only)	Customized
Program Implementation		
Call Occurrence	Continuous (daily; did it happen)	Twilio report
Call Connection	Continuous (daily; did the call connect to a person)	Twilio report
Call Duration	Continuous (daily); for every call placed, duration	Twilio report
Intracall dynamics	Continuous	Analysis of real-time audio streams

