#### To input text, click in the light grey area below.

Our primary outcome of interest is Hemoglobin A1C. However, the approach being used is modeled after a successful mental health intervention (Kahlon et al 2021) which showed depression can be improved with the type of empathy calls utilized in the current study.

To ensure that the effect of the empathy calls program on A1c can be assessed without confounding it with depressive mood in the first 6-month phase-I portion, we will rely on stratified randomization so that

approximately 50% (N=75) of the individuals in both the control and experimental group have a PHQ9  $\geq$ 5 at baseline and 50% of the individuals have PHQ9 <5 at baseline. With 150 individuals in each arm, three assessments for A1c, the primary outcome, and depression (PHQ9), secondary outcome, we have 80% statistical power with alpha = .05 to detect effects as small as f = .09, which is a small, standardized effect size, and have 90% power to detect effects as small as f = .10, also a small effect size, assuming only a moderate correlation for rank-order stability across time for each outcome of r = .30. This correlation is reasonable for A1c and is an underestimate for the typical correlation for PHQ9. Statistical power for the effect of interest increases as these correlations in the outcome measures goes up. Regarding correlations, we have 90% power to detect correlations as small as r = .26 and 80% power to detect correlations as small as r = .23 within each group (N = 150) at alpha = .05. These are fair to moderate effect sizes that bear on the power of any follow-up mediation analyses.

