We will test differences in the trajectory of A1c over the course of six-months with three assessments (baseline, 3- and 6-months) for those who receive empathy calls to support diabetes self-management versus those who do not receive these support calls. We will rely on linear mixed effect regressions with random terms to model individual differences in both the intercept and change terms, accounting for the clustering effect of shared lightly trained callers. We will predict these trajectories using the following person-level covariates: grouping indicator, terms to capture diabetic treatment type and dose, change in PHQ9 from baseline to 6-month depression. The cross-level interaction of grouping indicator with time will constitute the effect of interest. In addition, if change in depression predicts the person-specific slopes for A1c and does so more strongly for those in the intervention than control group, we would have evidence that depression management affects A1c course. Similar models will be constructed for the secondary outcome of depression, PHQ9 across three waves of data collection, with frequency/duration of support calls across those waves modeled as a time-varying covariate. Person-level covariates will include grouping indicator, terms to capture change in A1c from baseline to 6-months. If change in A1c predicts person-specific slopes for depression and does so more strongly for those in the intervention than control, we would have preliminary evidence that improved control of A1c affects course of depression, an unlikely outcome. The outcome of these mixed effect regressions will permit a preliminary estimate of the mediational role of depression on A1c management in phase-I. We will estimate those indirect effects using bootstrapped standard errors using the MPlus modeling framework for longitudinal change from baseline to 6-months. Healthcare utilization outcomes both self-reported and obtained from LSCC will be harmonized into a composite score of utilization. Depending on the distribution of each aspect of utilization (ER visits, hospitalization, PCP visits), we will construct models to predict differences between the intervention and control arm while covarying change in A1c and depression from baseline to 12-months.

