# d Inclusion Criteria

To input text, click in the light grey area below.

Adults aged 21 to 70 years old

A1c >=  $\geq$ 7.5 at baseline measurement and 8.0 at least one time in prior 12 months.

At least one visit with Lone Star Circle of Care within the past 12 months (in person or telehealth) Must be willing to answer the PHQ-9 form in its entirety at baseline data collection due to stratified randomization design.

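### The clinic-record part of the utilisation composite has no stated pre-randomisation value, and the utilisation models adjust for no baseline utilisation from either source, so this secondary comparison gives up precision

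*Combined protocol and SAP*

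**What the plan says.** The Measures table in Section 4 has two utilisation rows. The self-report row, "Healthcare Utilization (PCP & BH clinic, Hosp, ED visits", is scheduled at baseline and at 3, 6, 9 and 12 months. The record row, "Healthcare Utilization (PCP visits, BH visits", comes from the LSCC electronic health record and has no time points; its frequency entry is "Data pulls for data collected during program".

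In the Measures paragraph of Section 4 the secondary outcome is named as "self-reported healthcare utilization". Section 5 (Data Analysis) then brings in the record source: "Healthcare utilization outcomes both self-reported and obtained from LSCC will be harmonized into a composite score of utilization". For the analysis, depending on the distribution of each aspect of utilisation, "we will construct models to predict differences between the intervention and control arm while covarying change in A1c and depression from baseline to 12-months". No baseline utilisation term appears in that description.

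Section 13d requires every participant to have had at least one LSCC visit, in person or by telehealth, in the 12 months before entry.

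**The concern.** Use of care differs a good deal between people, and prior use is a natural predictor of later use. A trial that can measure prior use on the same definition as the outcome would normally adjust for it, because that removes between-person noise and chance imbalance between arms.

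Here the composite has two sources after randomisation and, on the plain reading of the table, one source before it. The two-source composite therefore cannot be formed at baseline as it will be formed at follow-up, and record-based visits have no baseline at all. The self-report baseline does exist, but Section 5 does not put it in the model. At stake is the precision of the utilisation comparison, and the risk that someone later computes change from a baseline that does not match the follow-up score.

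**Working it through.** **Step 1. Set the sources side by side.**

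| Source | Visit types | Before randomisation | After randomisation | Named as covariate in Section 5 |
|---|---|---|---|---|
| Self-report | PCP, BH, hospital, ED | Baseline | 3, 6, 9, 12 months | No |
| LSCC record | PCP, BH | None stated | Program period | No |
| Composite | Both sources merged | Self-report only | Both sources | No |

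Section 5 names ER visits, hospitalisation and PCP visits as the aspects of utilisation. Of these three, the record row covers only PCP visits.

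**Step 2. The plan's own power figures.** These concern A1c and PHQ-9, not utilisation. With N = 300, m = 3 assessments, ρ = 0.30 and the group-by-time interaction on 2 and 596 degrees of freedom, the noncentrality is λ = f²·N·m/(1 − ρ).

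- f = 0.10: λ = 0.01 × 900/0.70 = 12.86, power 0.903 (stated 90%).
- f = 0.09: λ = 0.0081 × 900/0.70 = 10.41, power 0.830 (stated 80%; the exact f for 80% is 0.0868, which rounds to 0.09).

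The stated figures reproduce after rounding. They give no SD, rate or correlation for utilisation, so everything below rests on assumed correlations.

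**Step 3. Value of one baseline covariate against none.** Adjusting for a covariate with correlation ρ to the outcome leaves a fraction 1 − ρ² of the variance. As a reference effect, take the one detectable with 80% power without adjustment at 150 per arm, two-sided 0.05: (1.960 + 0.842) × √(2/150) = 0.323 SD.

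| Assumed ρ | Residual variance | Power at 0.323 SD |
|---|---|---|
| 0 | 1.00 | 0.800 |
| 0.3 | 0.91 | 0.836 |
| 0.4 | 0.84 | 0.864 |
| 0.5 | 0.75 | 0.899 |
| 0.6 | 0.64 | 0.938 |

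For ρ from 0.3 to 0.6, adjustment removes 9% to 36% of the variance. Self-report alone could deliver a gain of this kind.

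**Step 4. Value of a record baseline on top of self-report.** Let s be the correlation of baseline self-report with the outcome, e that of the baseline record count, and c the correlation between the two. Then

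R² = (s² + e² − 2·s·e·c)/(1 − c²),

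and the further fall in residual variance is 1 − (1 − R²)/(1 − s²).

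| s | e | c | R², both | Further fall | Power, self-report only | Power, both |
|---|---|---|---|---|---|---|
| 0.5 | 0.4 | 0.6 | 0.266 | 2.1% | 0.899 | 0.905 |
| 0.5 | 0.5 | 0.8 | 0.278 | 3.7% | 0.899 | 0.909 |
| 0.4 | 0.5 | 0.6 | 0.266 | 12.6% | 0.864 | 0.905 |
| 0.5 | 0.6 | 0.7 | 0.373 | 16.3% | 0.899 | 0.943 |
| 0.3 | 0.5 | 0.5 | 0.253 | 17.9% | 0.836 | 0.900 |
| 0.4 | 0.6 | 0.6 | 0.363 | 24.1% | 0.864 | 0.939 |

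Worked for the fifth row: R² = (0.09 + 0.25 − 0.15)/0.75 = 0.253; residual variance 0.747 against 0.91, and 1 − 0.747/0.91 = 17.9%.

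The increment therefore runs from about 2% to 24%, depending mainly on whether the record predicts better than self-report. The formulas are linear-normal. Section 5 leaves the model to the distribution of each aspect, so for visit counts these figures are a guide only.

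**The case against.** The strongest reply is that the named secondary outcome is self-reported and already has a like-for-like baseline on one instrument covering all four visit types. That stands, and it limits the point. A reader might infer that chance imbalance in prior utilisation cannot be removed. The documents do not support that: baseline self-report can address it, imperfectly, once it is put in the model.

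A reader might also take the missing record baseline to be the best available predictor. Nothing in the documents ranks the sources, and a look-back in the same fields would give no baseline for hospital or ED use. Nor should the loss be stated as 1/0.91 = 1.10 to 1/0.64 = 1.56 times the participants. That range credits the record pull with the whole gain over no adjustment, when a self-report baseline is already collected.

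A further tempting reading is that the composite would show a spurious rise from baseline. That belongs to a change analysis the plan does not state. Section 5 compares arms, and the change terms it mentions are covariates for A1c and depression. How the composite is scored is also undefined.

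Two other objections stand in part. The frequency entry could describe when the pull is made rather than the dates it covers, and the LSCC data agreement is not among the documents; even so, no other place states the window. And Section 13d guarantees one visit, which under Section 4 may be of any type, not a year of LSCC history. Some participants would have a thin look-back.

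**Conclusion.** The point holds as a matter of precision on a secondary outcome. On the plain reading, the record component has no matching pre-randomisation value, and Section 5 adjusts for no baseline utilisation from either source. Randomisation protects the arm comparison from bias on this point.

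The larger and more certain improvement is to use the baseline self-report already in hand. The record look-back is a cheap addition whose benefit may be small (about 2%) or worthwhile (about 24% of residual variance). Both sizes rest on assumed correlations, on a linear approximation, and on 150 per arm with no allowance for dropout.

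**What to change.** 1. In Section 5, add to each utilisation model the baseline self-reported utilisation for the matching visit type (PCP, BH, hospital, ED).
2. In the Section 4 Measures table, state the record window explicitly: 12 months before randomisation through 12 months after, for PCP and BH visits, with the same visit definitions throughout. Add the pre-randomisation record count as a covariate for the PCP and BH outcomes and for the composite. Hospital and ED outcomes rely on the self-report baseline.
3. State that change in the composite will not be computed from a self-report-only baseline.

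Item 1 needs no new data. Item 2 needs a longer date range in a pull already planned, with revised data-agreement and authorisation wording; it adds no visits or participant burden. Participants with little LSCC history before enrolment should be identifiable, so that a short record is not read as low use. Section 62a has identifiers destroyed once the data are analysed, so the window should be settled while records can still be linked.

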# **5** Data Analysis

Describe the data analysis plan, including any statistical procedures or power analysis.

#### To input text, click in the light grey area below.

Our primary outcome of interest is Hemoglobin A1C. However, the approach being used is modeled after a successful mental health intervention (Kahlon et al 2021) which showed depression can be improved with the type of empathy calls utilized in the current study.

To ensure that the effect of the empathy calls program on A1c can be assessed without confounding it with depressive mood in the first 6-month phase-I portion, we will rely on stratified randomization so that

approximately 50% (N=75) of the individuals in both the control and experimental group have a PHQ9  $\geq$ 5 at baseline and 50% of the individuals have PHQ9 <5 at baseline. With 150 individuals in each arm, three assessments for A1c, the primary outcome, and depression (PHQ9), secondary outcome, we have 80% statistical power with alpha = .05 to detect effects as small as f = .09, which is a small, standardized effect size, and have 90% power to detect effects as small as f = .10, also a small effect size, assuming only a moderate correlation for rank-order stability across time for each outcome of r = .30. This correlation is reasonable for A1c and is an underestimate for the typical correlation for PHQ9. Statistical power for the effect of interest increases as these correlations in the outcome measures goes up. Regarding correlations, we have 90% power to detect correlations as small as r = .26 and 80% power to detect correlations as small as r = .23 within each group (N = 150) at alpha = .05. These are fair to moderate effect sizes that bear on the power of any follow-up mediation analyses.

We will test differences in the trajectory of A1c over the course of six-months with three assessments (baseline, 3- and 6-months) for those who receive empathy calls to support diabetes self-management versus those who do not receive these support calls. We will rely on linear mixed effect regressions with random terms to model individual differences in both the intercept and change terms, accounting for the clustering effect of shared lightly trained callers. We will predict these trajectories using the following person-level covariates: grouping indicator, terms to capture diabetic treatment type and dose, change in PHQ9 from baseline to 6-month depression. The cross-level interaction of grouping indicator with time will constitute the effect of interest. In addition, if change in depression predicts the person-specific slopes for A1c and does so more strongly for those in the intervention than control group, we would have evidence that depression management affects A1c course. Similar models will be constructed for the secondary outcome of depression, PHQ9 across three waves of data collection, with frequency/duration of support calls across those waves modeled as a time-varying covariate. Person-level covariates will include grouping indicator, terms to capture change in A1c from baseline to 6-months. If change in A1c predicts person-specific slopes for depression and does so more strongly for those in the intervention than control, we would have preliminary evidence that improved control of A1c affects course of depression, an unlikely outcome. The outcome of these mixed effect regressions will permit a preliminary estimate of the mediational role of depression on A1c management in phase-I. We will estimate those indirect effects using bootstrapped standard errors using the MPlus modeling framework for longitudinal change from baseline to 6-months. Healthcare utilization outcomes both self-reported and obtained from LSCC will be harmonized into a composite score of utilization. Depending on the distribution of each aspect of utilization (ER visits, hospitalization, PCP visits), we will construct models to predict differences between the intervention and control arm while covarying change in A1c and depression from baseline to 12-months.

For phase-II of the study, we have the opportunity to estimate two effects of interest including: a) the effect of the incentive and materials provision (2-selected items and health tool) on A1c among controls in phase-II over a period of 6-months compared to its effects when such provisions are coupled with empathy calls among intervention participants in phase-I (a between group effect estimate), b) the effects of exposure periods (phase-I and phase-II) on A1c and depression from baseline through 12-months separately for the two groups. In the case of the intervention group, the phase-I to phase-II difference gives clues to sustainability and in the case of the control group, the phase-I to phase-II difference provides a within-person estimate of the effect of incentive provision

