#### To input text, click in the light grey area below.

Design: Randomized controlled trial.

**Population**: Adults with Hemoglobin A1C >8.0 measured at any point in the 12 months prior to enrollment, who have had at least one visit (Family medicine, behavioral health or other) with Lone Star Circle of Care within the past 12 months (in person or telehealth)

**Randomization:** Consented participants will be randomized to the intervention or control arm in a 1:1 ratio.

[figure not shown]
**Blinding:** Research staff involved in taking biomedical measurements will be blinded to participant status. Participants will complete surveys in person using a tablet or individual paper copy, thus research associates will remain blinded.

Time period: The study is divided into two parts.

- *Phase 1 (6 months)* is a randomized controlled trial testing the effect of telephone call-based empathetic engagement supported by caller-customized letters, together with small self-selected incentives (health tool) and caller-selected personal recognitions (small gifts selected based on the callers understanding of the participant), and low-literacy basic diabetes self-management information, against usual care. The primary outcome is Hemoglobin A1C (A1C) with repeated measures at baseline, 3 and 6 months.
- *Phase 2 (subsequent 6 months)* is the follow-up phase allowing us to *estimate* the 12 month longer term trajectory of A1C in Intervention and Control. To maximize the utility of the study to inform the most effective program design, participants in the control arm will receive the same opportunity to self-select health tool as the intervention arm received in Phase 1, but will make the choice during the 6

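### Every participant has a clinic A1c from the year before enrolment that the analysis leaves unused; in a baseline-adjusted model it could remove about 5% of residual variance at r = .30

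*Combined protocol and SAP*

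**What the plan says.** Two places make a prior A1c a condition of entry. The population statement in Section 4 (Design and Methodology) reads "Adults with Hemoglobin A1C >8.0 measured at any point in the 12 months prior to enrollment". Section 13d (Inclusion Criteria) asks for a study-visit value of at least 7.5 and also "8.0 at least one time in prior 12 months". Sections 11, 17 and 19 say that the clinic network draws up the list of eligible patients, so the value should be in its records.

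Section 5 (Data Analysis) sets out the A1c model: "We will test differences in the trajectory of A1c over the course of six-months with three assessments (baseline, 3- and 6-months". The person-level covariates are "grouping indicator, terms to capture diabetic treatment type and dose, change in PHQ9 from baseline to 6-month depression". The test is stated as follows: "The cross-level interaction of grouping indicator with time will constitute the effect of interest". The prior A1c is neither a covariate nor a wave, and no other section gives it an analytic use.

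On access, Section 4 (Measure Collection) says: "Electronic Health Record measures will be collected via a data agreement with Lone Star Circle of Care (LSCC". The only row of the measures table sourced from that record covers primary care and behavioural health visits. The recruitment handover in Section 19 consists of names, e-mails and phone numbers.

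**The concern.** One finger-stick reading, taken in people admitted only at 7.5 or above, is a noisy and range-restricted measure of a person's usual A1c. A second reading made before randomisation can carry further information about 6-month A1c, and here it exists for everyone by rule. Because it predates randomisation, adjusting for it does not bias the treatment comparison. It also needs no extra visit or test. At stake is precision in the primary comparison. As the measures table stands, the analysts would not receive the value at all.

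**Working it through.** **Inputs from the documents.** 300 participants, 150 per arm; three A1c waves; alpha .05; f = .09 at 80% power and f = .10 at 90%; and "assuming only a moderate correlation for rank-order stability across time for each outcome of r = .30" (Sections 5 and 15).

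**Inputs the documents do not give (assumptions).** The correlation of the prior clinic A1c with baseline (r_PB) and with 6-month A1c (r_P6), and the mean and SD of A1c in the clinic population.

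**Step 1: the plan's own figures.** Take a repeated-measures within-between interaction with noncentrality f² × N × m / (1 − r), N = 300, m = 3, r = .30, and 2 and 596 degrees of freedom. The smallest detectable f is .0868 at 80% power and .0995 at 90%. These round to the stated .09 and .10, so the planning figures reproduce.

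**Step 2: baseline-adjusted 6-month A1c, all correlations equal to r.** R² is r² with baseline alone and 2r²/(1 + r) with baseline plus prior.
- At r = .30: .090 against .18/1.30 = .1385, a gain of .0485 of total variance.
- Residual variance ratio: (1 − .1385)/(1 − .090) = .947, a 5.3% reduction.
- In participants: 300 × (1 − .947) = 16 saved, or 300 × (1/.947 − 1) = 17 added.
- In power: a comparison with 80% has standardised signal 1.960 + 0.842 = 2.802. Dividing by √.947 gives 2.879, and Φ(2.879 − 1.960) is about 82%.
- At r = .50, .60 and .70 the residual reduction is 11%, 14% and 17%.

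**Step 3: unequal correlations.** Hold baseline-to-6-month and r_PB at .30. The gain in R² is (r_P6 − .09)²/.91.

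| r_P6 | Gain, total variance | Gain, residual variance |
|---|---|---|
| .30 | 4.8% | 5.3% |
| .25 | 2.8% | 3.1% |
| .20 | 1.3% | 1.5% |
| .15 | 0.4% | 0.4% |
| .09 (first-order decay) | 0% | 0% |

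**Step 4: the entry cuts.** I simulated equally correlated readings (population r .4 to .8; assumed clinic mean/SD 7.8/1.8 and 8.5/2.0) and kept those with prior ≥ 8.0 and baseline ≥ 7.5. The baseline-to-6-month correlation after selection was .24 to .65, and the residual variance ratio ran from .964 down to .853. If .30 instead describes unselected patients, the two cuts lower the gain to about 1.7% to 2.8% of total variance (assumed cut-offs from −0.5 to +0.5 SD).

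**Step 5: the model as written.** Section 5 treats baseline as an outcome wave and tests group by time. With arm baseline means free, the contrast rests on change from baseline, and the prior value's covariance with change is r_P6 − r_PB.
- Under equal correlations this is r − r = 0. The generalised least squares variance of the contrast at r = .30 is .018667 both with and without the prior value.
- After the entry cuts in Step 4, the residual variance ratio for change is .992 to .995, a gain of 0.5 to 0.8% (about 2 of 300).
- With arm baseline means constrained equal, the variance falls from .012133 to .011487 (5.3%) with categorical time, and from .01127 to .010431 (7.4%) with linear time.

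**The case against.** The strongest objection is that the gain does not attach to the analysis the plan specifies. That stands. A reader might infer that a second pre-randomisation reading helps however the study-visit baseline is handled. Step 5 shows otherwise: with baseline as a free outcome wave and equal correlations, it adds essentially nothing. The 5% is measured against a model that already adjusts for baseline or equates the arm baselines. The further step from a free to a constrained baseline (.018667 to .012133 at r = .30) is a separate gain and should not be credited to the prior A1c.

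A reader might also take 5% as a minimum. The documents do not support that. Their r = .30 concerns stability across study waves, and they give no correlation for a clinic value up to 12 months old. Step 3 shows how quickly the gain shrinks if that value tracks follow-up less well.

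Three smaller points also stand. The treatment type and dose terms already in the model may absorb part of the same variance. The most recent clinic value need not be the qualifying one and may lie below 8.0, so the simulation only approximates the proposed covariate. And leaving out an optional covariate is a legitimate choice.

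None of this removes the suggestion. Section 4 (Measures) names A1c at 6 months as the primary outcome, and a baseline-adjusted comparison addresses that directly. In that form the covariate is nearly free.

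**Conclusion.** The point holds as a modest, conditional gain in precision. Eligibility guarantees the value, the model does not use it and the extract does not list it. In a baseline-adjusted or equal-baseline model, the prior A1c removes about 5% of the residual variance of 6-month A1c if it correlates .30 with both baseline and follow-up, or about two points of power from 80%. Higher common correlations give more. A weaker link between the older value and follow-up gives 1.5% or close to nothing. For the model as written, the figure is about 0 to 1% under equal correlations. The 82% should not be read against the plan's own 80%, which belongs to the group-by-time test with baseline as a wave. Nothing in the plan is wrong or biased on this account.

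**What to change.** 1. Add the most recent pre-enrolment clinic A1c and its date to the existing record extract. A fixed rule is needed because the criterion accepts any qualifying value in the year.
2. State that the primary A1c model takes the study-visit baseline as a covariate, or constrains arm baseline means to be equal.
3. Pre-specify the prior A1c and its interaction with visit as covariates in that model, alongside the study-visit baseline.

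The cost is one extra field under the data agreement, one covariate with its interaction, and an explicit statement of how baseline is handled. Participants do nothing more. The downside is that record values of varying age, presumably from a laboratory, would sit beside finger-stick values. That affects only the size of the gain.
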